2.2 Prenatal Cardiac Imaging

Most cases of TGA in Ontario are nowadays detected before birth and referred to the Fetal Cardiac Program at the Hospital for Sick Children. All patients undergo repeated assessment before birth including a final fetal echocardiogram and a fetal MRI before delivery for prediction of the neonatal risk of severe cyanosis. This is standard care and not research-related.

Better prediction of the neonatal hemodynamics before birth would dramatically facilitate the perinatal care of babies with TGA but is not reliably obtained by conventional imaging.

The prenatal risk assessment of TGA is currently based on the two-dimensional and Doppler echocardiographic evaluation of the heart and in particular of possible shunts across the atrial septum, the ventricular septum, and the arterial duct. In the fetal circulation, the foramen ovale (FO) is an important provider of oxygenated umbilical blood from the placenta to the left heart. The crescent shaped FO, located in the central portion of the secundum atrial septum, progressively increases in width up to 6 mm at term. The thin, mobile septum primum is positioned on the left side of the atrial septum and functions as a flap valve of the FO. During most of the cardiac cycle, it is pushed into the left atrium (LA) by the steady stream of blood that enters the FO. The fetal echocardiographic evaluation of the atrial septum mainly relies on the size of the FO, the position, mobility and shape of the FO flap and the documentation of right-left shunting across the foramen ovale. The prenatal evaluation of the arterial duct includes the echocardiographic assessment of its diameter and documentation of ductal patency and flow direction by color and pulse wave Doppler imaging.

Fetal MRI offers a versatile set of additional tools to assess the fetal physiology and is routinely offered to parents at SickKids to examine the hemodynamic alterations of cardiac lesions and the

impact on the perfusion of organs such as the brain (6–8). Our center has significant experience with the clinical-research applications of MRI in the human fetus (9). This includes the application of fetal MRI in combination with MH (REB No 1000048468).

Importantly, MRI and echocardiographic imaging pose no known risks to the fetus and the mother.

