Limited information is available about the most appropriate amount of O₂ to be used for MH. Experimental data from animal and human subjects showed that increasing FiO₂ from room air to 40% resulted in the greatest increase in fetal PaO₂, and maximal effects on the fetal circulation. Furthermore, inhaled O₂ up to 15L/min is well tolerated via a simple face mask, which results in a FiO₂ of ~40 to 50%. While no adverse effects of chronic MH were reported when used to treat fetal growth restriction (14-16), a Cochrane review (11) of experimental animal data raised the possibility that chronic maternal hyperoxygenation could reduce uterine arterial blood flow, and thus recommended further investigations if chronic maternal O₂ was to be used for this indication. *This is not expected with acute hyperoxygenation. Effects on the arterial duct are also unlikely to occur due to the short duration of O₂ supplementation: it usually takes at least 1-2 days for spontaneous ductal closure at birth. Ductal constriction was not observed in any of the previous studies using MH (12).*

In this study, we will examine the added diagnostic value of acute MH in predicting neonatal maladaptation due to poor intracardiac mixing of oxygenated blood. MH (70% of O₂ by face mask) will be administered in late gestation at two separate occasions, during echocardiography and MRI. The rate and duration of MH (10 to 15L/min by mask for up to 30-45 minutes/test) is considered to be safe to the mother and her fetus. We know that if acute MH is used in the normal 3rd trimester fetus with a patent FO, this leads to pulmonary vasodilation, a 30-50% increase in pulmonary blood flow and in left atrial load, as well as a reduction in DA flow by

fetal MRI (13). Data on the acute effects of MH on fetal TGA are limited and no specific studies have been performed to study the response of the pulmonary vasculature to supplementary O₂. MRI data obtained without the use of MH in 4 fetuses with TGA/IVS and suspected RAS at SickKids (14) demonstrated significantly reduced flow across the FO, increased combined cardiac output, and increased flow in the ascending (AAo) and descending (DAo) aorta, UV, and aorto-pulmonary collaterals when compared with normal fetuses. The fetus with the lowest FO shunting and highest aorto-pulmonary collateral flow died from PPHN after birth.

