2.4 Study Rationale

To examine the baseline fetal hemodynamics as well as the response to acute MH as an added diagnostic test, we will combine various fetal echocardiographic and MR imaging tools. The prenatal findings will then be compared to the neonatal presentation.

We postulate that conditions that predispose newborns to acute neonatal compromise will be detectable and distinguishable prior to birth by echocardiography, MRI, or by combining the findings of both exams. We expect to encounter the following 4 clinical scenarios:

- 1) *TGA/IVS with unrestricted atrial shunting before and after birth:* we expect fetal baseline differences in LV/RV O₂ content and DAo/AAo O₂ content related to unrestricted right-left atrial shunting. MH is expected to further increase the differences in LV/RV O₂ content and DAo/AAo O₂ content, which leads to an increase pulmonary blood flow, LV preload and LV stroke volume due to O₂-mediated vasodilation of the pulmonary vasculature. As a confirmation of pulmonary vaso-reactivity to O₂, the branch PA pulsatility index will decrease by $\geq 10\%$ and this will coincide with lower peak systolic flow and reversal of end-diastolic flow across the DA.
- 2) *TGA/IVS with in-utero RAS:* In the absence of intracardiac shunting, RV/LV and DAo/AAo O₂ content will be equal at baseline and with MH and no significant effect on pulmonary flow will be observed.
- 3) *TGA/IVS with postnatal RAS:* RV/LV and DAo/AAo O₂ content will differ at baseline when the FO is still patent. With MH-induced functional closure of the FO by the septal flap, the RV load and AAo O₂ content will preferentially increase to reach an equal or higher oxygen content and saturation when compared with the LV, MPA, DA and DAo.
- 4) *TGA with PPHN:* supplementary maternal O₂ will not affect fetal pulmonary blood flow and PA pulsatility.

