8. STATISTICS

This is an observational cohort study to test whether acute MH is a useful diagnostic test for fetal TGA. This requires confirmation of the study concept that among TGA fetuses there will be specific hemodynamic and structural characteristics and responses that will be associated with neonatal compromise shortly after birth. Neonatal compromise is defined as any of these outcomes: pre-op/BAS mortality; minimal pre-BAS pH ≤ 7.1 , SaO₂ $\leq 40\%$, PaO₂ ≤ 25 mmHg, maximal serum lactate ≥ 10 mmol; and/or PPHN (combined pre-operative reverse differential cyanosis $\geq 30\%$ and/or postoperative RVp $\geq 75\%$ systemic ≥ 48 h post-surgery or $\geq 50\%$ at postoperative discharge). Twenty-two (31%) of 70 consecutive newborns born at Mount Sinai Hospital for fetal TGA/IVS fulfilled at least one of the outcomes ([name] et al. AEPC 2016). PPHT affects 1-3% of children with TGA. Based on these data we would expect about 35 cases without severe neonatal compromise, 15 cases with neonatal compromise and 1 case with PPHT.

Simple descriptive statistics will be adequate for this small feasibility and safety study. Data obtained from this study will further help to describe the possible ranges in hemodynamic findings at baseline and during MH in a larger cohort of TGA patients and in comparison with our previous data. The comparison between pre and post MH variables will be analysed using the Brand Altman's plot. Receiver operating statistics will be used to test the diagnostic value of MH.

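### The protocol rationale says the study examines what maternal hyperoxygenation adds diagnostically, but Section 8 plans an ROC of MH with no accuracy comparison against baseline imaging and no primary MH index, so added value is not estimated

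*Combined protocol and SAP*

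**What the plan says.** - **Rationale.** Section 2.3: "we will examine the added diagnostic value of acute MH in predicting neonatal maladaptation due to poor intracardiac mixing". Section 2.4 refers to "the response to acute MH as an added diagnostic test", to be examined alongside baseline hemodynamics.
- **Objective.** Section 4.1 is narrower. It asks how fetuses respond to MH and how that response is associated with neonatal outcome. It does not speak of added value.
- **Existing practice.** Section 2.2: "All patients undergo repeated assessment before birth including a final fetal echocardiogram and a fetal MRI before delivery for prediction of the neonatal risk". This is described as standard care. On the echo side, "The fetal echocardiographic evaluation of the atrial septum mainly relies on the size of the FO", together with features of the flap and the shunt.
- **Analysis.** Section 8 opens with "This is an observational cohort study to test whether acute MH is a useful diagnostic test for fetal TGA". It then plans descriptive statistics and two analyses. The first is "The comparison between pre and post MH variables will be analysed using the" Bland-Altman plot. The second is "Receiver operating statistics will be used to test the diagnostic value of MH". No index, modality, cut-off or baseline ROC is named.

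**The concern.** Added value needs a comparator, and Section 2.2 supplies an obvious one: the baseline imaging every patient already has. Neither planned analysis uses it. The Bland-Altman plot compares measured values before and during MH, not their accuracy for neonatal outcome. The ROC describes MH by itself.

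What is at stake is how the result can be used. A respectable AUC for MH would not tell the team whether the oxygen test tells them more than the scan done minutes earlier. Scenario 3 of Section 2.4 shows why this matters. There the foramen ovale (FO) is patent at baseline and the problem appears "With MH-induced functional closure of the FO by the septal flap". That is where MH should add most, and only a comparison with baseline can show it.

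**Working it through.** **1. The plan's own figure.** Section 8 takes 22/70 = 31.4% with neonatal compromise. For 50 participants, 50 × 22/70 = 15.7 and 50 × 48/70 = 34.3, against the stated 15 and 35. The split reproduces. The documents give no AUC, AUC difference, correlation or precision target, so every such value below is an assumption.

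**2. An AUC for MH alone does not determine the gain.** Take equal-variance normal markers that are independent within outcome groups, and let z = Φ⁻¹(AUC). Two such markers combine to AUC = Φ(√(z₁² + z₂²)).
- FO diameter by echo, assumed AUC 0.70: z = 0.524, z² = 0.275.
- Baseline MRI O₂-content difference, assumed AUC 0.75: z = 0.674, z² = 0.455.
- Suppose the MH change is simply proportional to the baseline MRI difference. Its own AUC is then 0.75, but it carries no new information.
- Added to FO diameter alone: Φ(√0.730) = Φ(0.854) = 0.80, an apparent gain of 0.10.
- Added to FO diameter plus baseline MRI: 0.80 before and 0.80 after, a gain of zero.
- If the change correlates with baseline MRI at r and is otherwise noise, its z is 0.674r. For r = 0.6 the AUC with FO diameter is Φ(√(0.275 + 0.164)) = 0.746, a gain of 0.05. For r = 0.8 it is Φ(√(0.275 + 0.291)) = 0.774, a gain of 0.07. Both gains are spurious.

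So a comparator is needed, and it must contain the same measure from the same modality. Otherwise a switch from echo to MRI passes for an effect of MH.

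**3. Carry-over if MH adds nothing.** With baseline AUC 0.75 and correlation r between baseline and during-MH values, the raw during-MH AUC is Φ(rz) and the change-score AUC is Φ(z√((1−r)/2)).
- r = 0.7: raw 0.68, change 0.60.
- r = 0.9: raw 0.73, change 0.56.

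Carry-over is large for raw values and small for changes. The change-score AUC also points in the direction opposite to the baseline marker.

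**4. Number of candidate measures.** Section 6.1.2 yields 7 echo measures (5 VTIs, branch-PA PI, DA flow ratio). Section 6.1.3 yields 7 calculated MRI flows and 3 O₂-content sites. That makes 17. Section 6.3 adds at least branch-PA VTI, MCA PI, UA VTI and UA PI, so there are at least 21. With no true signal, 15 v 35 and direction fixed, a single named index exceeds AUC 0.70 in about 1% of simulated datasets. The best of 7 does so in 7–8% and the best of 17 in 12–19% (between-measure correlation 0.5 to 0). This matters only if a best measure is picked and the number tried is not reported.

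**5. Precision of the paired difference at 15 v 35.** Hanley–McNeil: SE² = [A(1−A) + (n₁−1)(Q₁−A²) + (n₀−1)(Q₂−A²)]/(n₁n₀), with Q₁ = A/(2−A) and Q₂ = 2A²/(1+A).
- A = 0.70: (0.210 + 14 × 0.0485 + 34 × 0.0865)/525 = 0.00729, so SE = 0.085. At A = 0.80, SE = 0.075.
- SE of the difference = √(s₀² + s₁² − 2ρs₀s₁), where ρ is the assumed correlation between the two AUC estimates.

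| Assumed AUCs | ρ = 0.3 | ρ = 0.5 | ρ = 0.7 |
|---|---|---|---|
| 0.70 to 0.80: half-width (power) | 0.19 (18%) | 0.16 (24%) | 0.12 (36%) |
| 0.75 to 0.85: half-width (power) | 0.17 (20%) | 0.15 (27%) | 0.12 (40%) |

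Power is two-sided at 0.05. A separate simulation with bootstrap optimism correction gave half-widths of 0.15 and 0.13 for these two rows, with zero excluded in 23–24% of runs.

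**The case against.** The best defence is that this is a pilot whose formal objective concerns response and association, analysed descriptively, and an ROC of MH serves that. This stands as far as it goes. A reader might infer that the plan fails its primary objective. It does not: the explicit added-value wording is in Section 2.3, and the phrase in Section 2.4 could mean no more than an extra test. Pilot status limits the precision to expect, but it does not supply a comparison that the rationale says will be examined.

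Baseline findings are not ignored either. Section 2.4 says prenatal findings will be set against the neonatal presentation, and Section 8 mentions characteristics as well as responses. So one cannot say baseline accuracy is ruled out, only that no comparison is planned.

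Three other stronger readings are tempting:
- That a good MH AUC would largely be carry-over from baseline. This applies to raw during-MH values. Sections 2.4, 4.1 and 6.1.2 point to the response or percent change, where carry-over is small.
- That the plan invites reporting of the best measure. Nothing in it proposes that; the rates in step 4 are conditional.
- That the branch-PA PI fall of at least 10% in Section 2.4 is already the index. It is offered there as confirmation of vasoreactivity in scenario 1 and is not named for the ROC.

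It is also fair to say that both sets of data are kept, so the comparison could be made later. But an index chosen after outcomes are seen is less credible than one named beforehand.

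**Conclusion.** The concern holds in a limited form. Section 2.3 undertakes to examine added diagnostic value over imaging that is already standard care, and the analyses in Section 8, followed as written, do not estimate it. This rests on the text and needs no calculation. The plan should be changed, but the gap does not undermine the association objective.

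The sizes rest on assumed AUCs and correlations. An MH index with no new information can show an apparent gain of 0.05 to 0.10 over an echo-only comparator, and zero once the same baseline MRI measure is included. With about 15 events, a true gain of 0.10 would carry a 95% CI half-width of about 0.12 to 0.19. The 31% event rate comes from TGA with intact septum (TGA/IVS), whereas fetuses with VSD are also eligible. With 10 events the simulated half-width is 0.15 to 0.16, against 0.13 to 0.15 with 15.

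**What to change.** Add one paragraph to Section 8 before outcomes are analysed:

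- **Index.** Name one primary MH response index and its direction. An example is the change with MH in AAo minus MPA O₂ content, with a higher value pointing to compromise. Section 2.4 implies a rise in scenario 3 and no change in scenario 2. The fall in scenario 1 is an inference from its wording and should be written down as such. This index does not describe scenario 4 (about 1 case expected).
- **Comparator.** Include the same measure from the same modality before MH: here, baseline AAo minus MPA O₂ content together with baseline FO diameter. If an echo index such as percent change in branch-PA PI is chosen instead, compare it with baseline branch-PA PI plus FO diameter.
- **Estimate.** In the same fetuses, against neonatal compromise as Section 8 defines it, report the AUC of baseline, the AUC of baseline plus the MH index, and the paired difference with 95% CI and bootstrap optimism correction. State that this is estimation only.
- **Population.** State that the Section 2.4 predictions for the O₂-content index concern TGA/IVS. Report that subgroup as well as all fetuses, including those with VSD.
- **Other measures.** Label them exploratory and state how many were examined.

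The cost is small, because baseline and MH values are already collected in the same fetuses. The drawbacks are that fetuses without usable paired imaging drop out of the comparison, and that the estimate will be imprecise. It can inform the design of a later study but will not settle added value.

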5.2 Patient Numbers and Study Duration

Recruitment will be from the time of REB approval of this study to the time 50 patients have successfully completed the study. We follow approximately 30 women per year with a fetal

diagnosis of simple TGA, defined as TGA either with an intact ventricular septum or with ventricular septal defect(s) (VSD). The rate of pregnancy termination is low (<5%) as most affected babies do not carry a risk of significant non-cardiac disorders. Parents of a child with congenital heart disease are also highly motivated in participating in research that might help their or other children with the same condition and we anticipate that at least 80% of eligible women will be willing to participate in this research. Based on these assumptions, we anticipate being able to successfully recruit 50 participants within ≤ 2.5 years.

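### Section 8 plans a ROC analysis with no named index, direction, cut-off or internal validation, so anything selected from the 50 fetuses would be scored on the data that selected it

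*Combined protocol and SAP*

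**What the plan says.** Section 8 states the diagnostic analysis in full as "Receiver operating statistics will be used to test the diagnostic value of MH". The same section says "Simple descriptive statistics will be adequate for this small feasibility and safety study". It does not say which variable is the index, which direction counts as a positive test, how a cut-off is set, how findings are combined, whether confidence intervals are given, or how accuracy is validated.

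Section 2.4 (Study Rationale) postulates that the conditions behind neonatal compromise will be "detectable and distinguishable prior to birth by echocardiography, MRI, or by combining the findings of both exams", without a combination rule. It gives one numeric response threshold, a fall of at least 10% in branch pulmonary artery (PA) pulsatility index (PI). It also describes an expected oxygen pattern in which content in the ascending aorta (AAo) becomes equal to or higher than on the left-heart side. Section 8 refers to neither. Section 6.3 lists, on a simple count, roughly 40 or more echocardiographic and MRI variables recorded at baseline and during maternal hyperoxygenation (MH).

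On size, Section 5.2 recruits "to the time 50 patients have successfully completed the study". Section 8 bases its expected case count on this: "Twenty-two (31%) of 70 consecutive newborns born at Mount Sinai Hospital for fetal TGA/IVS fulfilled at least one of the outcomes". It concludes: "we would expect about 35 cases without severe neonatal compromise, 15 cases with neonatal compromise and 1 case with PPHT".

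**The concern.** A ROC analysis estimates accuracy fairly when index, direction and cut-off are fixed beforehand, or when the rule is scored on data that did not produce it. Here none of these is fixed for the ROC and no second cohort is planned. If a cut-off is chosen because it separates these cases best, a marker because it has the largest AUC, or a model because it was fitted to these outcomes, chance differences count as accuracy. With about 15 cases there is a lot of chance to exploit, and Section 6.3 supplies many candidates.

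At stake is how the result is read. Sections 1 and 8 both present the study as finding out whether MH is a useful diagnostic test. Section 2.5 looks ahead to counselling and perinatal care of future fetuses. An inflated accuracy figure would misinform the design of the next study and any later discussion of such use.

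**Working it through.** **Inputs.** N = 50 (Section 5.2). Compromise rate 22/70 (Section 8). PPHT rate: "PPHT affects 1-3% of children with TGA" (Section 8).

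**The plan's own figures.** 50 × 22/70 = 15.7 cases and 50 - 15.7 = 34.3 non-cases. PPHT: 50 × 0.01 = 0.5 to 50 × 0.03 = 1.5. These agree with the stated 15, 35 and 1. The three sum to 51 unless the PPHT case is counted within the 15, which the definition of compromise implies. The plan gives no power or precision calculation to reproduce.

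**Set-up.** Simulated data had 15 cases, 35 non-cases and normally distributed markers unrelated to outcome, so the true AUC is 0.50 and the true Youden J is 0.

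- AUC = (R - n1(n1+1)/2)/(n1·n0), where R is the rank sum of the cases, n1 = 15 and n0 = 35.
- J = sensitivity + specificity - 1 at the cut-off that maximises it, scored on the same 50.

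The Youden rule, the number of markers and their correlation are assumptions; the plan gives none of them. Markers are independent unless stated.

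**Apparent accuracy of markers with no signal (means).**

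| Selection made on the data | AUC | Sensitivity / specificity | J |
|---|---|---|---|
| One marker, direction fixed, best cut-off | 0.50 | 62% / 55% | 0.18 |
| One marker, direction free, best cut-off | 0.57 | 65% / 60% | 0.25 |
| Best of 5 markers | 0.64 | 69% / 64% | 0.33 |
| Best of 10 | 0.67 | 71% / 66% | 0.37 |
| Best of 20 | 0.69 | 73% / 67% | 0.40 |
| Logistic combination of 2 | 0.61 | 66% / 63% | 0.29 |
| Logistic combination of 3 | 0.64 | 68% / 65% | 0.33 |
| Logistic combination of 4 | 0.66 | 71% / 65% | 0.36 |
| Logistic combination of 8 | 0.74 | 76% / 71% | 0.47 |

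**Correlated markers.** The best of 10 has mean AUC 0.67, 0.655 and 0.63 at correlations 0, 0.5 and 0.8. The best of 25 has 0.70, 0.68 and 0.65. The range 0.65 to 0.70 for 10 to 25 markers thus covers correlations from 0 to 0.5; stronger correlation lowers it but does not remove the inflation.

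**Case count.** The 31% comes from fetuses with an intact ventricular septum, while Section 5.2 also admits those with ventricular septal defects. With 10 to 20 cases among 50, J for one marker with fixed direction runs from 0.20 down to 0.16, so the conclusion does not depend on exactly 15.

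**Effect of correction.** The bootstrap-corrected value is the apparent value minus the mean optimism. Optimism is the accuracy of the rule refitted in a resample, scored in that resample, minus the accuracy of the same rule in the original 50. Cut-off choice was repeated in each resample. On data with no signal:

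- one marker, direction free: AUC 0.56 to 0.51, J 0.23 to 0.07;
- two-marker combination: AUC 0.60 to 0.53, J 0.29 to 0.10;
- four-marker combination: AUC 0.66 to 0.55, J 0.36 to 0.13.

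For four markers the share of false accuracy removed is (0.66 - 0.55)/(0.66 - 0.50) = 69% for AUC and (0.36 - 0.13)/0.36 = 64% for J.

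**The case against.** The strongest reply is that the faulty procedure is inferred. A reader might conclude that the plan commits to data-driven cut-offs or a fitted multi-marker model. It does not: Section 8 mentions no optimal cut-off, selection step or regression, and the combination in Section 2.4 is a hypothesis. That stands. What remains is that nothing is fixed for the ROC and there is no other cohort, so a cut-off or combination, if one is reported, would most likely come from these 50 fetuses.

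Second, a reader might infer that any worthless index would look moderately accurate. The figures do not support that. One pre-specified index with fixed direction has mean AUC 0.50, and even at its best cut-off it shows only 62% / 55%. Values that look moderate need selection among about 10 or more markers, or a combination of about 4 or more.

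Third, a reader might take Section 2.4 as already fixing usable cut-offs. It does not. The 10% fall is given as confirmation of vasoreactivity in the unrestricted-shunt scenario, and no pulsatility response is stated for postnatal restriction. The aortic oxygen pattern is an expectation with no allowance for measurement error. Neither is linked to the composite outcome.

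Fourth, this is a pilot that calls descriptive statistics adequate. Section 2.5 speaks only of potential implications, and Section 6.1 says a mother's decision on participation does not affect perinatal management. This softens the consequence. It does not remove the bias, which comes from selecting and scoring on the same data, and Section 8 still calls the ROC a test of diagnostic value.

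**Conclusion.** The concern holds in conditional form: any cut-off, best marker or echo-MRI combination chosen from these 50 fetuses would be reported with optimistic accuracy, and Section 8 has no safeguard. Under no true signal the inflation is about 0.18 to 0.25 in J for one marker at its best cut-off. Mean apparent AUC is 0.65 to 0.70 for the best of 10 to 25 markers and 0.64 to 0.74 for a logistic combination of 3 to 8, against a truth of 0.50. These sizes rest on 15 cases against 35 non-cases, the Youden rule, assumed numbers of markers, and correlations of 0 to 0.5 for the best-of-many figures.

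The AUC of one pre-specified index with fixed direction is not inflated. Nor is a wide interval evidence of optimism. A true AUC of 0.75 with a Hanley-McNeil standard error of 0.081 gives 0.75 ± 1.96 × 0.081, or 0.59 to 0.91. That describes imprecision, which is a separate matter.

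**What to change.** Amend Section 8 before outcomes are seen.

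1. Name one primary MH response index with its direction, and report its AUC with a 95% confidence interval. If the Section 2.4 patterns (branch PA PI fall of at least 10%; AAo oxygen content equal to or above that of the left ventricle, main pulmonary artery and descending aorta) are adopted as pre-specified test criteria, say so, and report sensitivity and specificity with exact intervals. State that Section 2.4 did not set them as classifiers of the composite outcome.
2. For any data-derived cut-off, marker selection or echo-MRI combination, report bootstrap optimism-corrected AUC, sensitivity and specificity, repeating the whole selection in each resample.
3. Label these results exploratory estimates pending external validation, because the correction removes most but not all of the optimism.

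Limiting the number of terms in a combination, or using penalised regression, is a reasonable option but a matter of preference.

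The cost is SAP wording and a little programming, with no extra participants, visits or procedures. The downside is that the reported accuracy will be less favourable.
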